11.1.2 Disease Parameters

Measurable disease. Measurable lesions are defined as those that can be accurately measured in at least one dimension (longest diameter to be recorded) as ≥ 20 mm by chest x-ray or as ≥ 10 mm with CT scan, MRI, or calipers by clinical exam. All tumor measurements must be recorded in millimeters (or decimal fractions of centimeters).

Note: Tumor lesions that are situated in a previously irradiated area might or might not be considered measurable. This will be determined by the investigator, and documented in source.

Malignant lymph nodes. To be considered pathologically enlarged and measurable, a lymph node must be ≥15 mm in short axis when assessed by CT scan (CT scan slice thickness recommended to be no greater than 5 mm). At baseline and in follow-up, only the short axis will be measured and followed.

Non-measurable disease. All other lesions (or sites of disease), including small lesions (longest diameter <10 mm or pathological lymph nodes with ≥10 to <15 mm short axis), are considered non-measurable disease. Bone lesions, leptomeningeal disease, ascites, pleural/pericardial effusions, lymphangitis cutis/pulmonitis, inflammatory breast disease, and abdominal masses (not followed by CT or MRI), are considered as non-measurable.

Note: Cystic lesions that meet the criteria for radiographically defined simple cysts should not be considered as malignant lesions (neither measurable nor non-measurable) since they are, by definition, simple cysts.

'Cystic lesions' thought to represent cystic metastases can be considered as measurable lesions, if they meet the definition of measurability described above. However, if non-cystic lesions are present in the same patient, these are preferred for selection as target lesions.

Target lesions. All measurable lesions up to a maximum of 2 lesions per organ and 5 lesions in total, representative of all involved organs, should be identified as **target lesions** and recorded and measured at baseline. Target lesions should be selected on the basis of their size (lesions with the longest diameter), be representative of all involved organs, but in addition should be those that lend themselves to reproducible repeated measurements. It may be the case that, on occasion, the largest lesion does not lend itself to reproducible measurement in which circumstance the next largest lesion which can be measured reproducibly should be selected. A sum of the diameters (longest for non-nodal lesions, short axis for nodal lesions) for all target lesions will be calculated and reported as the baseline sum diameters. If lymph nodes are to be included in the sum, then only the short axis is added into the sum. The baseline sum diameters will be used as reference to further characterize any objective tumor regression in the measurable dimension of the disease.

Non-target lesions. All other lesions (or sites of disease) including any measurable lesions over and above the 5 target lesions should be identified as **non-target lesions** and should also be recorded at baseline. Measurements of these lesions are not required, but the presence, absence, or in rare cases unequivocal progression of each should be noted throughout follow-up.

11.1.3 Methods for Evaluation of Measurable Disease

All measurements should be taken and recorded in metric notation using a ruler or calipers. All baseline evaluations should be performed as closely as possible to the beginning of treatment and never more than 4 weeks before the beginning of the treatment.

The same method of assessment and the same technique should be used to characterize each identified and reported lesion at baseline and during follow-up. Imaging-based evaluation is preferred to evaluation by clinical examination unless the lesion(s) being followed cannot be imaged but are assessable by clinical exam.

Clinical lesions Clinical lesions will only be considered measurable when they are superficial (e.g., skin nodules) and palpable lymph nodes) and $\geq 10 \text{ mm}$ diameter as assessed using calipers (e.g., skin nodules). In the case of skin lesions, documentation by color photography, including a ruler to estimate the size of the lesion, is recommended.

Chest x-ray Lesions on chest x-ray are acceptable as measurable lesions when they are clearly defined and surrounded by aerated lung. However, CT is preferable.

Conventional CT and MRI This guideline has defined measurability of lesions on CT scan based on the assumption that CT slice thickness is 5 mm or less. If CT scans have slice thickness greater than 5 mm, the minimum size for a measurable lesion should be twice the slice thickness. MRI is also acceptable in certain situations (*e.g.* for body scans).

Use of MRI remains a complex issue. MRI has excellent contrast, spatial, and temporal resolution; however, there are many image acquisition variables involved in MRI, which greatly impact image quality, lesion conspicuity, and measurement. Furthermore, the availability of MRI is variable globally. As with CT, if an MRI is performed, the technical specifications of the scanning sequences used should be optimized for the evaluation of the type and site of disease. Furthermore, as with CT, the modality used at follow-up should be the same as was used at baseline and the lesions should be measured/assessed on the same pulse sequence. It is beyond the scope of the RECIST guidelines to prescribe specific MRI pulse sequence parameters for all scanners, body parts, and diseases. Ideally, the same type of scanner should be used and the image acquisition protocol should be followed as closely as possible to prior scans. Body scans should be performed with breath-hold scanning techniques, if possible.

Ultrasound Ultrasound is not useful in assessment of lesion size and should not be used as a method of measurement. Ultrasound examinations cannot be reproduced in their entirety for independent review at a later date and, because they are operator dependent, it cannot be guaranteed that the same technique and measurements will be taken from one assessment to the next. If new lesions are identified by ultrasound in the course of the study, confirmation by CT or MRI is advised. If there is concern about radiation exposure at CT, MRI may be used instead of CT in selected instances.

Endoscopy, Laparoscopy The utilization of these techniques for objective tumor evaluation is not advised. However, such techniques may be useful to confirm complete pathological response when biopsies are obtained or to determine relapse in trials where recurrence following complete response (CR) or surgical resection is an endpoint.

Tumor markers Tumor markers alone cannot be used to assess response. If markers are initially above the upper normal limit, they must normalize for a patient to be considered in complete clinical response.

Cytology, Histology These techniques can be used to differentiate between partial responses (PR) and complete responses (CR) in rare cases (*e.g.*, residual lesions in tumor types, such as germ cell tumors, where known residual benign tumors can remain).

The cytological confirmation of the neoplastic origin of any effusion that appears or worsens during treatment when the measurable tumor has met criteria for response or stable disease is mandatory to differentiate between response or stable disease (an effusion may be a side effect of the treatment) and progressive disease.

11.1.4 Response Criteria

11.1.4.1 Evaluation of Target Lesions

Complete Response (CR): Disappearance of all target lesions. Any pathological lymph nodes (whether target or non-target) must have reduction in short axis to <10 mm.

Partial Response (PR): At least a 30% decrease in the sum of the diameters of target lesions, taking as reference the baseline sum diameters.

Progressive Disease (PD): At least a 20% increase in the sum of the diameters of target lesions, taking as reference the smallest sum on study (this includes the baseline sum if that is the smallest on study). In addition to the relative increase of 20%, the sum must also demonstrate an absolute increase of at least 5 mm. (Note: the appearance of one or more new lesions is also considered progressions).

Stable Disease (SD): Neither sufficient shrinkage to qualify for PR nor sufficient increase to qualify for PD, taking as reference the smallest sum diameters while on study, including baseline. Note that patients are not able to go from PR to SD.

11.1.4.2 Evaluation of Non-Target Lesions

Complete Response (CR): Disappearance of all non-target lesions and normalization of tumor marker level. All lymph nodes must be non-pathological in size (<10 mm short axis).

Note: If tumor markers are initially above the upper normal limit, they must normalize for a patient to be considered in complete clinical response.

Non-CR/Non-PD: Persistence of one or more non-target lesion(s) and/or maintenance of tumor marker level above the normal limits.

Progressive Disease (PD): Appearance of one or more new lesions and/or *unequivocal progression* of existing non-target lesions. *Unequivocal progression* should not normally trump target lesion status. It must be representative of overall disease status change, not a single lesion increase.

Although a clear progression of "non-target" lesions only is exceptional, the opinion of the treating physician should prevail in such circumstances, and the progression status should be confirmed at a later time by the review panel (or Principal Investigator).

11.1.4.3 Evaluation of Best Overall Response

The best overall response is the best response recorded from the start of the treatment until disease progression/recurrence (taking as reference for progressive disease the smallest measurements recorded since the treatment started). The patient's best response assignment will depend on the achievement of both measurement and confirmation criteria.

For Patients with Measurable Disease (i.e., Target Disease)

Target Lesions	Non-Target Lesions	New Lesions	Overall Response
CR	CR	No	CR
CR	Non-CR/Non-PD	No	PR
CR	Not evaluated	No	PR
PR	Non-CR/Non-PD/not	No	PR
	evaluated		
SD	Non-CR/Non-PD/not	No	SD
	evaluated		
PD	Any	Yes or No	PD
Any	PD***	Yes or No	PD
Any	Any	Yes	PD

^{***} In exceptional circumstances, unequivocal progression in non-target lesions may be accepted as disease progression.

Note: Patients with a global deterioration of health status requiring discontinuation of treatment without objective evidence of disease progression at that time should be reported as "*symptomatic deterioration*." Every effort should be made to document the objective progression even after discontinuation of treatment.

For Patients with Non-Measurable Disease (i.e., Non-Target Disease)

Non-Target Lesions	New Lesions	Overall Response
CR	No	CR
Non-CR/non-PD	No	Non-CR/non-PD*
Not all evaluated	No	not evaluated
Unequivocal PD	Yes or No	PD
Any	Yes	PD

^{* &#}x27;Non-CR/non-PD' is preferred over 'stable disease' for non-target disease since SD is increasingly used as an endpoint for assessment of efficacy in some trials so to assign this category when no lesions can be measured is not advised

11.1.5 Duration of Response

Duration of overall response: The duration of overall response is measured from the time measurement criteria are met for CR or PR (whichever is first recorded) until the first date that recurrent or progressive disease is objectively documented (taking as reference for progressive disease the smallest measurements recorded since the treatment started).

The duration of overall CR is measured from the time measurement criteria are first met for CR until the first date that progressive disease is objectively documented.

Duration of stable disease: Stable disease is measured from the start of the treatment until the criteria for progression are met, taking as reference the smallest measurements recorded since the treatment started, including the baseline measurements.

11.1.6 Progression-Free Survival

PFS is defined as the duration of time from start of treatment to time of progression or death, whichever occurs first.

11.1.7 Overall Response Rate

The ORR is defined as the proportion of patients achieving complete response (CR) or PR as assessed by the Investigator per RECIST (v.1.1).

11.1.8 Response Review

Response review will be done by central review at the Princess Margaret Cancer Centre by a trained radiologist.

12. DATA REPORTING / REGULATORY REQUIREMENTS

Adverse event lists, guidelines, and instructions for AE reporting can be found in Section 7.0 (Adverse Events).

12.1 Data Collection and Reporting

All data obtained in the clinical trial described in this protocol will be reported on eCRFs in the Medidata Electronic Document Capture system (Medidata). Data reported on eCRFs should be consistent with the source documents and verifiable. All data for the primary and secondary endpoints will source verified prior to publication. The Investigator will review the data and electronically sign the eCRFs to acknowledge agreement with the data entered. Data will be entered into Medidata will be used for developing tables and listings for the final study report.

Prior to the start of the study, the Investigator will complete a Site Participant's Log showing the signatures and handwritten initials of all individuals who are authorized to make or change entries on source documents and eCRFs.

12.2 Source Documents

Source documents refer to the original documents, data, and records where the first recording of a data point occurred. Examples of source documentation include, but are not limited to:

Hospital records, clinical and office charts, laboratory notes, memoranda, subjects' diaries or evaluation checklists, pharmacy dispensing records, recorded data from automated instruments, copies or transcriptions certified after verification as being accurate copies, microfiches, photographic negatives, microfilm or magnetic media, x-rays, subject files, and records kept at the pharmacy, at the laboratories and at medicotechnical departments involved in the clinical trial)

Please ensure that source document entries are attributable, legible, contemporaneous, original, and accurate. Note that sign-off of source documents should be attributable to a single record and "bracketing" multiple entries on source document pages for a single signature is not allowed. Corrections to source document entries should only be completed by drawing a single line through the previous entry and then recording the corrected data, initialing the change, and dating the change. Only the individual that initially recorded the data should make any corrections.

12.3 Retention of Patient Records and Study Files

The ICH guidance document, Good Clinical Practice: Consolidated Guidelines (ICH Guidance Document E6) (1997) states that the investigator and sponsor shall retain study records relating to the study until at least 2 years after the last approval of a marketing application and until there are no pending or contemplated marketing applications, or at least 2 years have elapsed since the

formal discontinuation of clinical development of the investigational product. In the event of a trial discontinuation, sponsor records should also be kept for a minimum of 2 years. Per Health Canada, all original records should be maintained for 25 years after the above requirements are satisfied and the final report has been issued. Records contained in the Clinical Trial Application should be maintained on file for at least 25 years. We will comply with these regulations. The Sponsor will notify sites when documents are to be destroyed.

12.4 Site and Study Closure

Upon completion of the study, the following activities, when applicable, will be completed by the Central Office in conjunction with the Investigator, as appropriate:

- Collection of study materials (i.e., specimen collection kits, drug shippers, etc.)
- Data clarifications and/or resolutions
- Accounting, reconciliation, and final disposition of used and unused study medication
- Review of site study records for completeness

If the Sponsor- Investigator or appropriate regulatory officials identify conditions arising during the study that indicate that the study should be halted or that the study center should be terminated, this action may be taken after appropriate consultation among the Sponsor and Investigator. Conditions that may warrant termination of the study include, but are not limited to, the following:

- The discovery of an unexpected, serious, or unacceptable risk to the patients enrolled in the study
- A decision on the part of the Sponsor to suspend or discontinue testing, evaluation, or development of the product
- Failure of the Investigator to enroll patients into the study at an acceptable rate
- Failure of the Investigator to comply with pertinent regulations of appropriate regulatory authorities
- Submission of knowingly false information to the Sponsor, or appropriate regulatory authority
- Insufficient adherence to protocol requirements
- Refusal of the Investigator to supply source documentation of work performed in this clinical trial

Study termination and follow-up will be performed in compliance with the conditions set forth in the International Conference on Harmonisation (ICH) sixth efficacy publication (E6) on Good Clinical Practice, Section 4.12, ICH E6 4.13, ICH E6 5.20, and ICH E6 5.21.

13. STATISTICAL CONSIDERATIONS

13.1 Study Design/Endpoints

The rate of subject entry and escalation to the next dose level will depend upon assessment of the safety profile of patients entered at the previous dose level. Toxicity will be evaluated according to the NCI Common Terminology Criteria for Adverse Events (CTCAE), Version 4.0.

Up to six evaluable patients will be treated at a given dose level combination and observed for at least 4 weeks from start of treatment to assess toxicity for purposes of determining dose limiting toxicities (DLTs). When exactly 6 patients have been enrolled on a given dose level and it is unknown whether the MTD has been exceeded or not, accrual will be suspended until enough toxicity data are available to decide (i.e. to determine if the dose level has at least 2 DLTs versus less than 2).

13.1.1 Phase I Study Design

A rolling six phase I design [47] will be used to accelerate the process of finding the maximum tolerated dose of hydroxychloroquine in combination with itraconazole given that these two drugs have been extensively studied and registered for other indications and that no drug-drug interactions are known to exist.

The starting dose of hydroxychloroquine of 200mg PO BID has been chosen as this is a clinically active dose in other disease entities and the maximum dose we wish to safely achieve is 600mg PO BID as studied in other cancer sites in combination with other anti-cancer therapies such as temsirolimus [33].

Dose-limiting toxicities have been defined in section 5.2. The rules for dose assignment and determination of MTD and RP2D are described in section 5.3.

13.1.2 Phase II study design

Once the dose level for hydroxychloroquine and combination itraconazole has been determined, the cohort will be expanded in a single-centre, single-arm, Simon two-stage design.

The phase II cohort will consist of a maximum of additional 34 patients. If 1 response is observed after 9 patients have been treated at RP2D, then an additional 25 patients will be enrolled.

CT scans will be performed every 8 weeks regardless of dosing delays.

The phase II cohort will serve to investigate ORR based on RECIST criteria (refer to).

13.1.3 Study Endpoints

The primary endpoint will be the maximum tolerated dose (or maximum administered dose) of hydroxychloroquine in combination with -300 mg PO BID of itraconazole for the recommended phase II dose.

The secondary endpoint of PFS and ORR have been defined in section 11.1.6 and 11.1.7 respectively.

13.2 Sample Size/Accrual Rate

The sample size will be a maximum of 52 patients. This will encompass between 6 and 18 on phase I and 34 on for the phase II component.

Phase II sample size:

Stage 1 of accrual: 9 response evaluable patients will be entered in the first stage. Using response hypotheses of H_0 <15 % and H_a >35%, we would reject the drug at the end of the first stage of accrual if no objective responses were seen. Otherwise, an additional 25 patients will be accrued. Patients treated at RP2D in the phase 1 part of the study will be considered for the statistical analysis of the phase 2 stage 1. A total (between phase 1 and phase 2 stage 1) of 9 response evaluable patients treated at RP2D are required.

Stage 2 of accrual: An additional 25 patients will be accrued. We would accept the drug as active if 8 or more objective responses are observed from 25 patients accrued.

Significance level and power: The procedure described above test the null hypothesis that the response rate is 15% versus alternating hypotheses that the response rate is 35%. The significance level (*i.e.*, the probability of rejecting H0 when it is true) is α =0.05 and the power (*i.e.*, the probability of deciding the regimen is active) is 0.81 when true response rate is 20%. The expected sample size with this design is 19 when the null hypothesis is true and 25 when the alternative hypothesis is true.

Accrual and Duration of Study

The estimated accrual for this study is 2-4 patients a month. Thus, patient accrual is expected to be completed within 12-18 months. Additional time is required to allow the response data to mature.

All of the patients registered in the study will be accounted for. The number of patients who were not evaluable, who died or withdrew before treatment began will be specified. The distribution of follow-up time will be described and the number of patients lost to follow-up will be given.

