5.3.2 Recommended Phase II Dose

The MTD is defined as the dose at which $\geq 2/3$ or $\geq 2/6$ patients experience dose limiting toxicity.

The dose one level below the MTD will be considered the RP2D. If the maximum tolerated dose is not reached on the phase I trial, the maximum administered dose will be the RP2D, which will be used for the purposes of the phase 2 cohort.

Up to a total of 6 patients may be treated at the recommended dose to assure information on the safety profile at that dose is complete.

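### The maximum of 52 patients and the 34 further phase II patients ignore the phase I patients who count toward phase II, and 18 months of accrual does not follow from 2 patients a month

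*Protocol*

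**What the plan says.** Protocol section 13.2 gives the overall size and its parts: "The sample size will be a maximum of 52 patients", and "This will encompass between 6 and 18 on phase I and 34 on for the phase II component". Section 13.1.2 describes the phase II part as new patients: "The phase II cohort will consist of a maximum of additional 34 patients". Its next sentence, however, speaks of 9 patients treated at the RP2D followed by 25 more.

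Section 13.2, repeated in the Synopsis, pools the two phases at the RP2D: "Patients treated at RP2D in the phase 1 part of the study will be considered for the statistical analysis" of stage 1. It fixes the size of that stage across both phases: "A total (between phase 1 and phase 2 stage 1) of 9 response evaluable patients treated at RP2D are required". If stage 1 is passed, "an additional 25 patients will be accrued". Section 5.3.2 bounds the phase I contribution: "Up to a total of 6 patients may be treated at the recommended dose". The Synopsis lists 6-18 patients for phase I and 9-34 for phase II, without saying that the two ranges overlap.

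On timing, section 13.2 estimates 2-4 patients a month and concludes that "patient accrual is expected to be completed within 12-18 months".

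**The concern.** The total of 52 is right only if no patient belongs to both phases. The pooling rule in section 13.2 says that some do. Under that rule, the 34 of the two-stage design already contains the evaluable phase I patients at the RP2D. Section 13.1.2 places all 34 on top of phase I.

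A site or coordinating office that follows section 13.1.2 could enrol up to six patients more than the design uses. It would then be unclear which patients at the RP2D form the analysed set. The accrual period matters less, because no decision rule depends on it. It is nevertheless presented as following from the stated rate, and at the lower end of that rate it does not.

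**Working it through.** **Inputs**
- Phase I maximum: 18 (section 13.2). Section 5.3 allows up to 6 at each of dose levels 1, 2 and 3, and 3 x 6 = 18.
- Stage 1: 9 response-evaluable patients at the RP2D, phase I patients included. Stage 2: 25 more (section 13.2).
- Phase I patients at the RP2D: up to 6 (section 5.3.2).
- Accrual: 2-4 patients a month (section 13.2).

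**The plan's own figure.** 18 + 34 = 52. It reproduces, but only with the phases treated as disjoint.

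**Counting the overlap once.** Let m be the number of phase I patients at the RP2D who are response evaluable, m = 0 to 6.
- Total analysed at the RP2D: 9 + 25 = 34.
- New phase II patients: (9 - m) + 25 = 34 - m.
- Overall maximum: 18 + (34 - m) = 52 - m.

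| m | New phase II patients | Overall maximum |
|---|---|---|
| 0 | 34 | 52 |
| 3 | 31 | 49 |
| 6 | 28 | 46 |

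If phase I does reach 18, all three levels hold six patients, so whichever of them becomes the RP2D has six. The value of m then depends only on how many of those six meet the definition of evaluable for response in section 11.1.1.

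**Section 13.1.2 taken literally.** 6 + 34 = 40 patients at the RP2D, against the 34 that section 13.2 analyses.

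**Accrual.** Months = patients / monthly rate.

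| Patients | 4 a month | 3 a month | 2 a month |
|---|---|---|---|
| 46 | 11.5 | 15.3 | 23.0 |
| 52 | 13.0 | 17.3 | 26.0 |

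At 2 a month, 18 months gives 2 x 18 = 36 patients. Finishing within 18 months needs 46/18 = 2.6 or 52/18 = 2.9 patients a month. These times exclude the accrual holds in sections 5.3.1 and 13.1 and any wait for stage 1 responses.

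**Type I error if 40 were analysed (conditional illustration).** At a true response rate of 15%, the probability of accepting the drug is the sum, over stage 1 counts x that allow continuation, of P(X1 = x) x P(X2 >= c - x). Here X1 is binomial on 9 patients, X2 is binomial on the later patients, and c is the number of responses needed. I take the rule that stops at 1 or fewer of 9 and accepts on 9 or more in all. With 25 later patients this gives 0.047, and its power at 35% is 0.81, in line with the stated alpha of 0.05 and power of 0.81. With 31 later patients (40 in all) it gives 0.097. The protocol does not state this rule.

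**The case against.** The strongest reply is that the operative rules already fix the test at 34. Section 13.2 sets stage 1 at nine across both phases, and the sentence after the disputed one in section 13.1.2 also runs from 9 to 25 more. That stands. A reader might infer that a 40-patient test is planned, but this requires one word in section 13.1.2 to override section 13.2. Section 13.5.2 bases the main response analysis on all eligible patients, so extra patients at the RP2D, once enrolled, could not simply be set aside. That makes the analysed set ambiguous; it does not make 40 the plan.

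A reader might also infer that type I error is inflated as the protocol stands. The documents do not support that. The rise from 0.047 to 0.097 needs both the literal reading and a cut-off that the protocol does not contain. Under the written rule (stop at 0 of 9, then 8 or more responses from the 25), type I error at 15% is 0.020. It is 0.023 even with six extra patients in stage 1: (1 - 0.85^15) x P(at least 8 of 25).

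A third tempting inference is that 46 is the correct cap. It is not. Evaluability for dose-limiting toxicity (section 5.2) and for response (section 11.1.1) are defined differently. A phase I patient can count for the first and not for the second, and stage 1 then needs another patient. A fixed cap of 46 could leave the design short, and 52 is a valid conservative ceiling.

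On accrual, it is fair to say that 12-18 months is a planning estimate, that 3 a month falls inside it, and that stopping after stage 1 would shorten it. What remains is that full enrolment at the stated lower rate does not fit.

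**Conclusion.** The point holds as a contradiction in the stated sample size and a failed upper limit on accrual. The figure of 34 is the total analysed at the RP2D, so calling it additional to phase I in section 13.1.2 conflicts with section 13.2. The expected maximum is 52 - m, that is, 46 to 52, and new phase II enrolment is 28 to 34. The possible excess is at most six patients.

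For 46-52 patients the lower end of the accrual estimate is about right (11.5-13 months at 4 a month). The upper end is short by 5 to 8 months (23-26 against 18, at 2 a month), before holds.

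The figures assume that phase I fills all three levels with six patients each, that enrolment runs to the end of stage 2, and that no patients are added to replace withdrawn or non-evaluable ones. The effect on type I error is a conditional risk of following section 13.1.2 literally, not a property of the planned test.

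**What to change.** - **Section 13.1.2:** delete the word additional before 34. State a total of 34 response-evaluable patients at the RP2D, including the m from phase I, so that 34 - m are new. The further 25 of stage 2 stay as they are.
- **Section 13.2:** give the overall maximum as 52 - m, that is, 46 with full overlap and no more than 52, with m defined as the number of response-evaluable phase I patients at the RP2D.
- **Synopsis:** use the same statement, and note that the phase I and phase II ranges overlap.
- **Accrual:** restate as about 12-26 months at 2-4 patients a month, plus holds for toxicity assessment and for the stage 1 decision.

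The cost is wording only. No analysis changes, enrolment can fall by up to six patients compared with section 13.1.2 as written, and the stated duration becomes longer.

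### The stage-1 futility rule (stop only at 0 responses in 9) does not produce the stated expected sample size of 19 under H0; stopping at 0 or 1 in 9 does

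*Protocol*

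**What the plan says.** Section 13.2 (Sample Size/Accrual Rate) sets the null response rate at 15% and the alternative at 35%. For stage 1, "9 response evaluable patients will be entered in the first stage", and "we would reject the drug at the end of the first stage of accrual if no objective responses were seen". If at least one response is seen, stage 2 opens: "Otherwise, an additional 25 patients will be accrued". The Synopsis repeats this rule.

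Section 13.1.2 (Phase II study design) words it independently and agrees: "If 1 response is observed after 9 patients have been treated at RP2D, then an additional 25 patients will be enrolled".

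For this procedure, 13.2 and the Synopsis claim a significance level of 0.05, power of 0.81 and these expected sizes: "The expected sample size with this design is 19 when the null hypothesis is true and 25 when the alternative hypothesis is true". No section gives a rule of stopping at 1 or fewer responses in 9.

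**The concern.** In a two-stage design the expected sample size under H0 is fixed by the null rate, the two stage sizes and the stage-1 boundary. The final cut-off plays no part in it. All four inputs are in the protocol, so the stated 19 can be checked directly against the written boundary, and it does not follow from it.

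The boundary is the instruction that will be followed at the interim look, and the protocol gives it consistently. That look exists to limit the number of patients treated with an ineffective regimen. If the boundary is one response too low, the trial delivers well under half of the early stopping that an expected size of 19 implies, and anyone who approved the trial on that figure was given one that the rule does not deliver.

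**Working it through.** **Inputs, all from section 13.2:** p0 = 0.15; p1 = 0.35; n1 = 9; stage 2 adds 25, so n = 34; stop if X1 ≤ r1, with r1 = 0 as written.

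**Formulas**

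- Probability of early termination: PET(p) = P(X1 ≤ r1), with X1 ~ Binomial(9, p)
- Expected size: EN(p) = 9 + 25 × (1 − PET(p))
- Probability of accepting the drug: the sum over x1 > r1 of P(X1 = x1) × P(X2 ≥ c − x1), with X2 ~ Binomial(25, p) and c the number of responses required in all 34

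**Step 1. What 19 requires.** Solving 9 + 25 × (1 − PET) = 19 gives PET = (34 − 19)/25 = 0.60.

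**Step 2. The written rule, r1 = 0.** PET(0.15) = 0.85^9 = 0.2316. EN(0.15) = 9 + 25 × 0.7684 = 28.21. The stated 19 is not reproduced.

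**Step 3. One response higher, r1 = 1.** PET(0.15) = 0.85^9 + 9 × 0.15 × 0.85^8 = 0.2316 + 0.3679 = 0.5995. EN(0.15) = 9 + 25 × 0.4005 = 19.01. The stated 19 is reproduced.

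**Step 4. Other variants.** r1 = 2 gives EN(0.15) = 12.5. Reading 25 as the total size with r1 = 0 gives 9 + 16 × 0.7684 = 21.3. Neither is 19.

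**Step 5. Alpha and power over all 34 patients**

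| Stage-1 stop | Final acceptance | Alpha (15%) | Power (35%) | EN (15%) | EN (35%) |
|---|---|---|---|---|---|
| 0 of 9 | ≥8 of 34 | 0.121 | 0.933 | 28.2 | 33.5 |
| 0 of 9 | ≥9 of 34 | 0.057 | 0.880 | 28.2 | 33.5 |
| 0 of 9 | ≥10 of 34 | 0.024 | 0.797 | 28.2 | 33.5 |
| 0 or 1 of 9 | ≥8 of 34 | 0.095 | 0.850 | 19.0 | 31.0 |
| 0 or 1 of 9 | ≥9 of 34 | 0.047 | 0.811 | 19.0 | 31.0 |

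If the final rule is read literally, as 8 or more among the 25 stage-2 patients alone after a 0-of-9 stop, alpha is 0.020 and power 0.68. EN(0.15) is still 28.2.

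**Step 6. Search.** Among two-stage designs with p0 = 0.15, p1 = 0.35, alpha ≤ 0.05 and power ≥ 0.80 (total size 20 to 41), the lowest EN under H0 belongs to n1 = 9, stop at ≤1, n = 34, accept at ≥9, with EN = 19.01. Its stage sizes are the protocol's own 9 and 25.

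**Step 7. Consequence: probability of going on to 25 more patients**

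| True response rate | Stop at 0 of 9 | Stop at 0 or 1 of 9 |
|---|---|---|
| 5% | 37% | 7% |
| 10% | 61% | 23% |
| 15% | 77% | 40% |
| 35% | 98% | 88% |

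**The case against.** The 0-of-9 rule is stated consistently in the Synopsis, 13.2 and, in different words, 13.1.2, while no section states a rule of 1 or fewer. On that view the error may lie in the operating characteristics and not in the boundary. The same sentence of 13.2 also gives 25 as the expected size under H1, which the 0-or-1 rule does not reproduce (31.0). The power of 0.81 is attached in the text to a true rate of 20%. The match to alpha and power needs a final cut of 9 of 34, whereas the protocol says "We would accept the drug as active if 8 or more objective responses are observed from 25 patients accrued". Finally, 77% against 40% holds at exactly 15%, the upper edge of H0, and response rate is a secondary endpoint.

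Much of this stands as a limit on certainty. The intended rule is inferred. The alpha comparison of 0.057 with 0.047 applies only if the final cut is 9 of 34, and the written final cut is a separate defect. The 25 under H1 fits neither boundary with 34 patients (33.5 or 31.0), so it cannot arbitrate between them.

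None of it removes the contradiction. The expected size under H0 is 28.2 for the written boundary whatever the final cut. At lower true rates the gap between the two rules persists, as the table shows. The rule decides whether 25 more patients are enrolled, whatever the rank of the endpoint.

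**Conclusion.** The concern holds. The written stage-1 rule and the stated expected size of 19 contradict each other: the rule gives 28.2. At a true response rate of 15%, early stopping has probability 0.232 under the written rule and 0.599 under the rule that yields 19, and the difference in expected size is 28.2 − 19.0 = 9.2 patients.

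The contradiction rests only on exact binomial probabilities and the protocol's own 15%, 9 and 25. That stopping at 0 or 1 of 9 was intended is a reconstruction. It is strongly supported, because that rule with acceptance at 9 or more of 34 meets the stated alpha, reproduces both 19 and 0.81 (the latter at 35%), and is the design with the lowest expected size under H0 at these rates. This must be fixed before the interim decision is taken.

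**What to change.** Restate stage 1 in 13.2, 13.1.2 and the Synopsis: stop if 0 or 1 of the first 9 evaluable patients respond, and enrol the further 25 only if 2 or more respond. In the same edit, state the final cut over all 34 patients as 9 or more, attach the power of 0.81 to a true rate of 35%, and replace the expected size of 25 under H1 with 31. The boundary and the figures then describe one design.

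If the sponsor does want to stop only at 0 of 9, keep that wording and restate the operating characteristics: expected size 28 under H0 and 33 under H1. The final cut must then be chosen again. At 9 of 34, alpha is 0.057 and power 0.88, which exceeds the protocol's own 0.05; at 10 of 34, alpha is 0.024 and power 0.797, just under 0.80.

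The cost is protocol wording only, with no change to the maximum sample size. The price of the higher boundary is that the chance of stopping early at a true 35% rate rises from 2% to 12%, a loss already included in the stated power of 0.81.
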